12.6. Appendix 6: Clinical Laboratory Tests

- The tests detailed in [Table 4](#) will be performed by the local laboratory.
- Protocol-specific requirements for inclusion or exclusion of participants are detailed in [Section 6](#) of the protocol.
- Additional tests may be performed at any time during the study as determined necessary by the investigator or required by local regulations.

Table 4 Protocol-Required Safety Laboratory Assessments

Laboratory Assessments	Parameters			
Haematology	Platelet Count		RBC Indices:	White blood cells (WBC) count with Differential:
	Red blood cell (RBC) Count		Mean corpuscular volume (MCV)	Neutrophils
	Hemoglobin		Mean corpuscular haemoglobin (MCH)	Lymphocytes
	Hematocrit		Mean corpuscular haemoglobin concentration (MCHC)	Monocytes
				Eosinophils
				Basophils
Clinical Chemistry ¹	Urea	Potassium	Aspartate aminotransferase (AST) (serum glutamic-oxaloacetic transaminase) (SGOT)	Triglycerides
	Creatinine	Sodium	ALT (Serum glutamic pyruvic transaminase) (SGPT)	Total bilirubin
	Glucose, fasting	Calcium	Alkaline phosphatase	Total Protein
	Uric Acid	Chloride	Gamma GT	Albumin
		Phosphate	Cholesterol	Globulin
Routine Urinalysis	
 • dipstick test: protein, blood, ketones, glucose, bilirubin, urobilinogen, leukocyte esterase, specific gravity, nitrites, pH; • Microscopic examination (if leukocyte esterase, nitrites, blood or protein is abnormal) 			
Other Screening Tests	
 • HIV • Hepatitis B (HBsAg) • Hepatitis C (Hep C antibody) • Alcohol, cotinine and drug screen (to include at minimum: amphetamines, barbiturates, cocaine, opiates, cannabinoids and benzodiazepines) 			

NOTES :

1. Details of liver chemistry stopping criteria and required actions and follow-up assessments after liver stopping or monitoring event are given in Section 8.1.1 and [Appendix 4](#) All events of ALT $\geq 3 \times$ upper limit of normal (ULN) and bilirubin $\geq 2 \times$ ULN ($>35\%$ direct bilirubin) or ALT $\geq 3 \times$ ULN and international normalized ratio (INR) >1.5 , if INR measured, which may indicate severe liver injury (possible Hy's Law), must be reported as an SAE (excluding studies of hepatic impairment or cirrhosis).
2. Local urine testing will be standard for the protocol unless serum testing is required by local regulation or IRB/IEC.

12.7. Appendix 7: Protocol Amendment History

The Protocol Amendment Summary of Changes Table for the current amendment is located directly before the Table of Contents (TOC).

**Description:**

- The purpose of this RAP is to describe the planned analyses and output to be included in the Clinical Study Report for Protocol 206764.
- This RAP is intended to describe the safety and pharmacokinetic analyses required for the study.
- This RAP will be provided to the study team members to convey the content of the Statistical Analysis Complete (SAC) deliverable.

## 1. INTRODUCTION

The purpose of this reporting and analysis plan (RAP) is to describe the analyses to be included in the Clinical Study Report for Protocol:

Revision Chronology:		
2017N324843_00	09-AUG-2017	Original
2017N324843_01	30-OCT-2017	
Protocol Amendment 1 was put in place to:
 
 
• Respond to comments from the Regulatory Authority: Medicines and Healthcare Products Regulatory Authoring.
 
• Reflect an update to the Investigator's Brochure (IB) published since approval of the original protocol.
 

## 2. SUMMARY OF KEY PROTOCOL INFORMATION

### 2.1. Changes to the Protocol Defined Statistical Analysis Plan

There were no changes or deviations to the originally planned statistical analysis specified in the protocol amendment 1 [(Dated: 30/Oct/2017)], however additional PK parameters have been requested.

### 2.2. Study Objective(s) and Endpoint(s)

Objective	Endpoint
Primary	

 
• To determine total radioactivity (drug related material) in plasma following a single IV microtracer of [C]-GSK2269557 (concomitant with an inhaled non-radiolabelled GSK2269557 dose) and a single oral dose of [C]-GSK2269557.
 
	
 
• AUC (0-inf), AUC (0-t), Cmax, tmax, t1/2 of total drug-related material (radioactivity) in plasma.
 

 
• To determine the rate and extent of excretion of total radioactivity in urine and faeces and the total recovery of radioactivity following a single IV microtracer of [C]-GSK2269557 (concomitant with an inhaled non-radiolabelled dose) and a single oral dose of [C]-GSK2269557.
 
	
 
• Urinary and faecal cumulative excretion as a percentage of the total radioactive dose administered over time.
 

Objective	Endpoint
Secondary	

 
To determine parent GSK2269557 concentration in plasma following a single IV microtracer of [C]-GSK2269557 concomitant with an inhaled non-radiolabelled GSK2269557 dose and a single oral dose of [C]-GSK2269557.
 
	
 
AUC(0-inf), AUC(0-t), Cmax, tmax, and t1/2 of parent GSK2269557 and [C]-GSK2269557 in plasma.
 
Volume and clearance of parent [C]-GSK2269557 after IV dose only.
 

 
To estimate the absolute bioavailability of GSK2269557 following inhaled and oral administration.
 
	
 
Oral and inhaled F (absolute bioavailability).
 

 
To evaluate the safety and tolerability of GSK2269557 after single IV, oral and inhaled doses in healthy participants.
 
	
 
Incidence of adverse events.
 
Laboratory safety, electrocardiogram (ECG) and vital signs parameters.
 

Exploratory	

 
To generate samples that will be used to characterise the metabolic profile of GSK2269557 in plasma, urine, faeces, and duodenal bile (following IV dose only), following a single IV microtracer of [C]-GSK2269557 (concomitant with an inhaled non-radiolabelled dose) and a single oral dose of [C]-GSK2269557 (these analytical investigations will be conducted and the results reported under a separate Platform Technology Services (PTS) In vitro/In vivo Translation (IVIVT), GlaxoSmithKline protocol).
 
	
 
Characterisation and quantification of metabolites in plasma, urine, faeces, and duodenal bile (these analytical investigations will be conducted and the results reported in a separate GSK PTS IVIVT protocol).
 

1. For measured concentrations of GSK2269557 in blood plasma, the nomenclature [C]-GSK2269557 describes the parent GSK2269557 concentration derived via analysis by liquid chromatography (LC) + Accelerator Mass Spectrometry (AMS), whereas GSK2269557 describes the parent GSK2269557 concentration derived via liquid chromatography-tandem mass spectrometry (LC/MS).

Note: the above table is as presented in the protocol amendment, subsequently additional PK parameters have been requested including: plasma AUC(0-24) and %AUCex for parent GSK2269557 and total radioactivity analytes; plasma ML(iv), ML(po), Fg, EH, Fabs; parent GSK2269557/ total radioactivity ratios for the plasma PK parameters Cmax, AUC(0-t), AUC(0-24) and AUC(0-∞); and CLR derivations are described in Section 8.

## 2.3. Study Design

Overview of Study Design and Key Features			
Screening  Within 30 days before first dose	Treatment Period 1  [  C]-GSK2269557 by IV infusion (concomitant with GSK2269557 by inhalation).  Sample collection for 7 days after dosing	At least 14 days washout between doses	Treatment Period 2  Single oral dose of [  C]-GSK2269557.  Sample collection for 7-14 days after dosing*

*If radioactivity excretion is higher than 1% upon discharge, faecal samples will be collected by participants at home after Day 15 (day of discharge/follow-up).
			
Design Features	
 
open-label
 
single centre
 
non-randomised
 
2-period single-sequence crossover
 
mass balance study
 
approximately 6 healthy male participants will be enrolled
 
there will be a washout period of at least 14 days between doses
 
		
Dosing	
 
The investigational drug is nemiralisib (GSK2269557). Each subject will receive a 10 µg radiolabelled version of GSK2269557 ([C]-GSK2269557) microtracer administered by IV infusion, concomitant with an inhaled non-radiolabelled 1000 µg dose of GSK2269557, in period 1 and a single 800 µg dose of [C]-GSK2269557 administered as an oral dose in period 2.
 
		
Time & Events	
 
Refer to Appendix 2: Schedule of Activities
 
		
Treatment Assignment	
 
This is an open label, non-randomised, 2-period single-sequence crossover study.
 
All subjects will receive [C]-GSK2269557 administered as a single IV dose (concomitant with an inhaled non-radiolabelled dose) at period 1 followed by [C]-GSK2269557 administered as a single oral dose at period 2
 
		

## 2.4. Statistical Hypotheses / Statistical Analyses

- No formal hypotheses will be tested or treatment comparisons performed. Data will be summarised using descriptive methods only.

### 3. PLANNED ANALYSES

#### 3.1. Final Analyses

The final planned primary analyses will be performed after the completion of the following sequential steps:

1. All subjects have completed the study as defined in the protocol
2. All required database cleaning activities have been completed and final database release (DBR) and database freeze (DBF) has been declared by Data Management.  
Note: pharmacokinetic concentration and pharmacokinetic parameter raw file generation start after GSK DBF – take approx. 18 working days after DBF. All other datasets available at DBF.

### 4. ANALYSIS POPULATIONS

Population	Definition / Criteria	Analyses Evaluated
All Participants Enrolled (APE) Population	
 
• All participants for whom a record exists on the study database; includes both screened participants and participants who are not screened but sign the informed consent form (ICF).
 
	
 
• Screen Failure
 

Safety Population	
 
• Participants in the APE Population who receive at least one dose of study treatment.
 
• Participants will be analysed according to the treatment they actually received
 
	
 
• Study Population
 
• Safety
 

Pharmacokinetic (PK) Population	
 
• Participants in the APE Population who receive at least one dose of study treatment and for whom a PK sample was obtained and analysed.
 
• Participants will be analysed according to the treatment they actually received
 
	
 
• PK
 

Refer to [Appendix 9](#): List of Data Displays which details the population used for each display.

#### 4.1. Protocol Deviations

Important protocol deviations (including deviations related to study inclusion/exclusion criteria, conduct of the trial, patient management or patient assessment) will be summarised and listed.

Protocol deviations will be tracked by the study team throughout the conduct of the study in accordance with the Protocol Deviation Management Plan.

- Data will be reviewed prior to freezing the database to ensure all important deviations are captured and categorised on the protocol deviations dataset.
- This dataset will be the basis for the summaries and listings of protocol deviations.

A separate summary and listing of all inclusion/exclusion criteria deviations will also be provided. This summary will be based on data as recorded on the inclusion/exclusion page of the pCRF.

The study endpoints will be reported using the populations detailed in Section 4 of this document regardless of whether the subjects deviate from the protocol.

If there are subjects with protocol deviations that may potentially impact the PK endpoints, exploratory sensitivity summaries may be considered. If further summaries of the data are produced, they will be detailed in the clinical study report.

## 5. CONSIDERATIONS FOR DATA ANALYSES AND DATA HANDLING CONVENTIONS

### 5.1. Study Treatment & Sub-group Display Descriptors

Treatment Group Descriptions			
		Data Displays for Reporting [1]	
Code	Description	Description	Order [2]
A	GSK2269557 1000 mcg Inhaled + [14C]-GSK2269557 10 mcg IV	557 IH + 14C-557 IV	1
B	[14C]-GSK2269557 800 mcg Oral	14C-557 ORAL	2

**NOTES:**

1. The following footnote will be presented on each display:  
557 IH + 14C-557 IV = Intravenous radiolabelled 10 mcg GSK2269557 co-administered with inhaled 1000 mcg GSK2269557; 14C-557 ORAL = 800 mcg radiolabelled GSK2269557 administered orally
2. Order represents treatments being presented in TFL, as appropriate

### 5.2. Baseline Definitions

For all endpoints (except as noted in baseline definitions) the baseline value will be the latest pre-dose assessment with a non-missing value, including those from unscheduled visits. If time is not collected, Day 1 assessments are assumed to be taken prior to first dose and used as baseline. Baseline definitions defined in the table are applicable to each “period” for this crossover study.

Parameter	Study Assessments Considered as Baseline			Baseline Used in Data Display
	Screening	Day -1	Day 1 (Pre-Dose)	
Safety				
12-Lead ECG	X	X	X	Day 1 (Pre Dose)
Vital Signs	X	X	X	Day 1 (Pre Dose)
Haematology	X	X	X	Day 1 (Pre Dose)
Clinical Chemistry	X	X	X	Day 1 (Pre Dose)
Liver Function	X	X	X	Day 1 (Pre Dose)

Unless otherwise stated, if baseline data is missing no derivation will be performed and baseline will be set to missing. The mean of triplicate measurements at any given time point will be used as the value for that time point unless otherwise stated.

### 5.3. Other Considerations for Data Analyses and Data Handling Conventions

Other considerations for data analyses and data handling conventions are outlined in the appendices:

Section	Component
11.3	Appendix 3 Study Phases and Treatment Emergent Adverse Events
11.4	Appendix 4 Data Display Standards & Handling Conventions
11.5	Appendix 5 Derived and Transformed Data
11.6	Appendix 6 Reporting Standards for Missing Data
11.7	Appendix 7 Values of Potential Clinical Importance

## **6. STUDY POPULATION ANALYSES**

### **6.1. Overview of Planned Study Population Analyses**

The study population analyses will be based on the “Safety” population, unless otherwise specified.

Study population analyses including analyses of subject’s disposition, protocol deviations, demographic and baseline characteristics, prior and concomitant medications, and exposure and treatment compliance will be based on GSK Core Data Standards. Details of the planned displays are presented in [Appendix 9 List of Data Displays](#).

## 7. SAFETY ANALYSES

The safety analyses will be based on the “Safety” population, unless otherwise specified.

### 7.1. Adverse Events Analyses

Adverse events analyses including the analysis of adverse events (AEs), Serious (SAEs) and other significant AEs will be based on GSK Core Data Standards. The details of the planned displays are provided in [Appendix 9](#) List of Data Displays.

### 7.2. Adverse Events of Special Interest Analyses

A comprehensive list of MedDRA terms based on clinical review will be used to identify each type of event. The details of the planned displays are provided in [Appendix 9](#) List of Data Displays.

### 7.3. Clinical Laboratory Analyses

Laboratory evaluations including the analyses of Chemistry laboratory tests, Haematology laboratory tests, Urinalysis, and liver function tests will be based on GSK Core Data Standards. The details of the planned displays are in [Appendix 9](#) List of Data Displays.

### 7.4. Other Safety Analyses

The analyses of non-laboratory safety test results including ECGs and vital signs will be based on GSK Core Data Standards, unless otherwise specified. The details of the planned displays are presented in [Appendix 9](#) List of Data Displays.

## 8. PHARMACOKINETIC ANALYSES

The plasma pharmacokinetic concentrations will have different nomenclatures dependent on the method of measuring. For measured concentrations of GSK2269557 in blood plasma, the nomenclature [C]-GSK2269557 describes the parent GSK2269557 concentration derived via analysis by liquid chromatography (LC) + Accelerator Mass Spectrometry (AMS), whereas GSK2269557 describes the parent GSK2269557 concentration derived via liquid chromatography-tandem mass spectrometry (LC/MS). It is expected that, for period 1, the radiolabelled iv dose will be measured using LC+AMS and will be labelled “[C]-GSK2269557”, the non-radiolabelled inhaled dose will be measured using LC/MS and will be labelled “GSK2269557”. For period 2, the radiolabelled oral dose will be measured using LC/MS and will be labelled “GSK2269557”. For each period the total radioactivity will be measured by AMS and will be labelled “Total Radioactivity”. However, these methods may be adapted if necessary.

The reconciliation of the PK Case Report Form (CRF) and SMS2000 data will be performed by, or under the direct auspices of, Clinical Pharmacology Science and Study Operations (CPSSO), GlaxoSmithKline.

Derivation of plasma pharmacokinetic parameters for [C]-GSK2269557, total radioactivity and GSK2269557 will be performed by, or under the direct auspices of, Clinical Pharmacology Modelling and Simulation (CPMS), GlaxoSmithKline.

Derivation of urine/faeces total radioactivity parameters will be performed by, or under the direct auspices of Bioanalysis, Immunogenicity and Biomarkers (BIB), PTS IVIVT, GlaxoSmithKline.

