6. Sampling times relative to the start of the IV infusion. Blood samples for total radioactivity, [¹⁴C]-GSK2269557 analysis and cold GSK2269557 analysis will be taken: pre-dose and at 0h (post inhalation and pre-IV infusion), at the end of infusion and at 0.33, 0.5, 0.75, 1, 2, 3, 4, 6, 8, 12, 16, 24, 48, 72, 96 and 168 h after the start of infusion.
7. Background radiation sample taken at screening, Day -1 and pre-dose only.
8. An additional pre-dose blood sample may be taken from 1 participant for preparation of a plasma shipment control (details provided in the SRM).
9. Blood samples for plasma metabolite profiling will be collected at 0.5 h and 4 h after the start of the IV infusion.
10. An aliquot from each urine collection will be taken for metabolic profiling (separate study).
11. Sampling times relative to the start of the IV infusion. Urine will be collected at pre-dose, 0-6 h, 6-24 h then over 24 h collection periods as follows: 24-48 h, 48-72 h, 72-96 h, 96-120 h, 120-144 h, 144-168 h.
12. An aliquot from each homogenised faecal collection will be taken for metabolic profiling (separate study).
13. Sampling times relative to the start of IV infusion. The pre-dose faecal collection sample can be collected up to 24 h pre-dose. Afterward faeces will be collected over 24 h collection periods as follows: 0-24 h, 24-48 h, 48-72 h, 72-96 h, 96-120 h, 120-144 h, 144-168h.
14. Entero-Test string device will be swallowed at approximately 3.5 h pre-dose (start of inhaled dose) while participants are in a fasted state and the string removed at about 2.5 h post-dose on Day 1. At about 0.5 h post-dose (i.e. 2 hours before string withdrawal) a food cue will be used to stimulate gall bladder emptying).

15. Meal times are 30 min, 4 h and 10 h post dose on Day 1. On all other days, meals will be served at the standard times for the unit.
16. AEs and SAEs will be collected from the signing of the ICF until the follow-up visit. However, any SAEs related to study participation or a GSK concomitant medication will be recorded from the time a participant consents to participate in the study and until the final follow-up visit contact.

Schedule of activities for treatment period 2

Procedure	Treatment Period 2 (Oral dosing)									Follow-up (7-14 days post-last dose) ^{2,3}	
	Day										
	-1	1 ¹		2	3	4	5	6	7		
		Pre-dose	Post-dose 0-16 h	24 h	48 h	72 h	96 h	120 h	144 h	168 h	
Admission to Unit	X										
Discharge from Unit ^{2,3}									X		

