1. Using the geometric mean measured exposed individual based on study 201544 (200 µg top dose Day 1) to generate (linear extrapolation including an increase of 1.71 fold for C_{max} and 1.54-fold on AUC due to formulation differences) the exposure for a 1000 µg Inhaled dose concomitant with a 10 mcg intravenous dose (15 min infusion) (intravenous dose exposures assume 1% of inhaled exposure as worst case) based on a single dose period 1 and following a single oral dose of 800 µg in period 2 (assuming 60:40 lung to oral deposition using study data from 201544 and charcoal block and linear extrapolation). C_{max} and AUC_{0-24h} of 3.5 ng/mL and 14.7 ng.h/mL for Period 1 and a C_{max} and AUC_{0-24h} of 0.47 ng/mL and 3.7 ng.h/mL for Period 2 respectively.
2. Based on the no observed adverse event level (NOAEL) derived from the rat 3 month toxicology study R29876 with a C_{max} and AUC of 43.7 ng/mL and 286 ng.h/mL respectively.
3. Based on the highest achieved geometric mean value derived from reported trials to date of 5.3 ng/mL and 85 ng.h/mL based on exposure on Day 7 following repeat daily single doses (study PII115117).

For more detailed information on the clinical pharmacokinetics, see the GSK2269557 IB [GlaxoSmithKline Document Number [2012N141231_07](#)].

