7.1. Treatments Administered

Study treatment			
Study Treatment Name:	[¹⁴ C]-GSK2269557 solution for IV infusion	GSK2269557 Ellipta DPI	[¹⁴ C]-GSK2269557 oral solution
Dosage formulation:	[¹⁴ C]-GSK2269557 hemisuccinate salt (GSK2269557T) in normal saline	GSK2269557 hemisuccinate salt (GSK2269557H) blended with lactose and magnesium stearate ¹ packed in foil blisters	[¹⁴ C]-GSK2269557 hemisuccinate salt (GSK2269557T) in water
Unit dose strength(s)/ Dosage level(s):	10 µg [¹⁴ C]-GSK2269557 (<0.5 µCi) in 10 mL	500 µg GSK2269557 per inhalation / 1000 µg dose	800 µg [¹⁴ C]-GSK2269557 (approximately 50 µCi) in 10 mL
Route of Administration:	IV infusion	Oral Inhalation	Oral
Dosing instructions:	Non-sterile powder is to be dissolved aseptically in 0.9% sodium chloride v/w to a concentration of 1 µg/mL free base equivalent. IV solution is prepared by sterile filtration. 20 mL will be withdrawn into Individual labelled participant specific 60 mL syringes. Only 10 mL of IV solution, equivalent to 10 µg GSK2269557 is then administered intravenously as a single dose over 15 minutes, as soon as possible (within 5 minutes) after the start of the inhaled dose	Inhale TWICE from this Inhaler, as directed.	Non-sterile powder is to be dissolved in sterile water to a concentration of 80 µg/mL. 10 mL of the solution, equivalent to 800 µg, is then administered as a single oral dose. Participants can have up to 250 mL water to wash the dose down
Packaging and Labelling	Labelled drug substance will be provided in High Density Polyethylene (HDPE) containers with polypropylene closure to the site pharmacy.	Study Treatment will be provided in a foil overwrap. Each foil overwrap will be labelled as required per country requirement.	Labelled drug substance will be provided in HDPE containers with polypropylene closure to the site pharmacy.
Manufacturer	GSK	GSK	GSK
Device:		ELLIPTA™ inhaler	

1. Magnesium stearate 0.4% w/w of total drug product

For more information on the preparation of the oral and IV dosing solutions, please refer to the Study Reference Manual (SRM).

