10. STATISTICAL CONSIDERATIONS

10.1. Sample Size Determination

No formal sample size calculation has been performed for this study. The primary objective of the study is to gain a better understanding of the compound's excretory and metabolic profile and 4-6 participants are deemed sufficient for this purpose (Penner, 2009). 6 participants will be enrolled into the study in order to achieve at least 4 completed participants.

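### LC/MS parent AUCs enter Inhaled F and Oral F with no isotope accounting: Inhaled F reads up to 1.0 percentage point high, and Oral F may read well low, depending on an assay property the documents do not state

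*SAP*

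**What the plan says.** SAP section 8 assigns an assay to each dose. In Period 1 the IV parent is expected by LC+AMS, under the name [14C]-GSK2269557, while "the non-radiolabelled inhaled dose will be measured using LC/MS and will be labelled" GSK2269557. For the oral dose the text is "For period 2, the radiolabelled oral dose will be measured using LC/MS and will be labelled" GSK2269557. Total radioactivity is by AMS in both periods.

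SAP Table 1 defines both absolute bioavailabilities as a dose-normalised LC/MS AUC divided by the dose-normalised LC+AMS AUC of the IV dose. Radiometric doses are used for oral and IV, and the nominal dose for inhaled. ML(po), Fg and the oral parent/total-radioactivity ratios use the same oral parent values. No formula has a term for isotopic composition.

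The Period 1 arm is "GSK2269557 1000 mcg Inhaled + [14C]-GSK2269557 10 mcg IV". Protocol section 7.1 gives the oral solution as 800 µg with "approximately 50 µCi) in 10 mL". The protocol schedule lists blood for both parent assays; the Period 1 footnote reads "analysis and cold GSK2269557 analysis will be taken: pre-dose and at 0h", and the Period 2 footnote repeats the pairing of a [14C] and a cold assay.

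Neither document says which isotopologues LC/MS detects. Protocol section 9.5.5 leaves assay detail to the Study Reference Manual. SAP section 8, the Oral F notes in Table 1 and section 8.3.4.1 allow the method to change, but none states a correction.

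**The concern.** The [14C] product is a mixture of labelled and unlabelled molecules, and the stated activities imply that the labelled share is substantial.

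- **Period 1.** Unlabelled molecules from the IV dose are chemically and isotopically the same as inhaled drug. LC/MS cannot separate them, yet Inhaled F attributes the whole LC/MS AUC to inhalation.
- **Period 2.** All oral drug comes from the labelled batch. A tandem mass spectrometry assay set on the unlabelled mass would miss the labelled molecules, while Dose(oral) counts the whole dose.

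At stake is the secondary bioavailability endpoint, together with ML(po), Fg and the oral parent/total ratios. Those ratios go into a mixed model with 95% confidence intervals. A constant multiplicative loss of parent would shift the estimate and both limits alike, and residual plots would not reveal it.

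**Working it through.** **Plan's own figures.** 0.6 × 37 = 22.2 kBq IV and 50 × 37 = 1850 kBq oral. The sum is 1872.2 kBq (Protocol section 5.5.2: about 1873). Multiplied by 0.4 mSv/MBq this is 0.749 mSv (stated: 0.75). The activities are consistent within that section.

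**Inputs from the documents.** Doses: 1000 µg inhaled, 10 µg IV, 800 µg oral. Activity: 50 µCi oral. IV activity is 0.6 µCi in the Synopsis and Protocol sections 5.1.2 and 5.5.2, but below 0.5 µCi in section 7.1, so both are carried through.

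**Assumptions not in the documents.** Molecular weight (MW) 300-600; one 14C per labelled molecule; maximum 14C specific activity 62.39 mCi/mmol (half-life 5730 years); dose-linear kinetics.

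**Labelled fraction L** = (µCi/µg × MW) / 62.39.

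- Oral: 50/800 = 0.0625 µCi/µg, so L = 0.0625 × MW / 62.39.
- IV at 0.6 µCi: 0.06 µCi/µg, so L = 0.06 × MW / 62.39.
- IV at 0.5 µCi: 0.05 µCi/µg, so L = 0.05 × MW / 62.39.

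**Inhaled F.** Let u be the share of IV parent that LC/MS detects. The observed value is F + u × 10/1000 = F + 0.01u. If all isotopologues are read, u = 1 and the bias is 1.0 percentage point. If only unlabelled drug is read, u = 1 − L(IV).

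**Oral F.** If only unlabelled drug is read, the observed value is F × (1 − L(oral)). If all isotopologues are read, it is F.

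Results if LC/MS reads only unlabelled drug:

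| MW | L oral | Oral F read/true | L IV, 0.6 µCi | Inhaled F bias, points | L IV, 0.5 µCi | Inhaled F bias, points |
|---|---|---|---|---|---|---|
| 300 | 0.301 | 0.699 | 0.289 | 0.71 | 0.240 | 0.76 |
| 400 | 0.401 | 0.599 | 0.385 | 0.62 | 0.321 | 0.68 |
| 500 | 0.501 | 0.499 | 0.481 | 0.52 | 0.401 | 0.60 |
| 600 | 0.601 | 0.399 | 0.577 | 0.42 | 0.481 | 0.52 |

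With two 14C atoms per labelled molecule the oral L halves to 0.15-0.30.

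**Relative size for Inhaled F.** The 1.0-point ceiling is 2% of a true F of 0.5, 3.3% of 0.3 and 10% of 0.1.

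**Quantities derived from oral parent, unlabelled-only reading.** With a true parent/total AUC ratio r, the observed ratio is r(1 − L), ML(po) becomes 1 − r(1 − L), and Fg falls by rL. For r = 0.5 and L of 0.3 to 0.6:

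- the ratio reads 0.35 to 0.20;
- ML(po) reads 0.65 to 0.80 instead of 0.50;
- Fg falls by 0.15 to 0.30.

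Fabs divides Oral F by Fg, so the two falls partly offset.

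**The case against.** The strongest case against is that nothing shows the assay misses labelled drug. The documents define GSK2269557 by the method, not as unlabelled mass, and the SAP assigns LC/MS to the radiolabelled oral dose on purpose. The word cold is a sample label, carried over from Period 1 where the inhaled drug really is unlabelled. This stands. A reader might infer that Oral F is biased downward as a matter of fact; the documents make that plausible but do not establish it.

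A reader might also infer that the SAP has dropped the [14C] parent assay in Period 2. It has not. Section 8 states an expectation and allows adaptation, section 8.1.2 lists all three analytes by treatment period, section 8.3.4.1 allows either parent name for the oral dose, and SAP Appendix 2 keeps the samples. What is missing is a rule for choosing the method and any correction if LC/MS is kept.

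The Period 1 bias is small. The study is descriptive, the inhaled dose is nominal, and Protocol section 10.1 says "No formal sample size calculation has been performed for this study". This supports treating Period 1 as the lesser part, but the bias is always upward and can be removed with data already planned.

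A third tempting step is to fault footnote 1 to Protocol Table 1, "intravenous dose exposures assume 1% of inhaled exposure as worst case". That is an assumption in the exposure-margin estimates and enters no bioavailability formula, so it forms no part of this point.

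**Conclusion.** The point holds as a gap in specification, with one certain small bias and one conditional bias that could be large.

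- **Certain in direction:** Inhaled F is too high by at most 1.0 percentage point. If LC/MS reads only unlabelled drug, the excess is about 0.4-0.7 points at 0.6 µCi IV, or 0.5-0.8 points at 0.5 µCi.
- **Conditional:** if LC/MS reads only unlabelled drug, Oral F and the oral parent/total ratios are about 30-60% too low in relative terms (15-30% with two 14C atoms), ML(po) is too high and Fg too low. If it reads all isotopologues, these biases are zero.

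The 1.0-point ceiling needs only the two mass doses and dose-linear kinetics. The other ranges also rest on the assumed molecular weight and number of 14C atoms. Oral F and the quantities built on the oral parent are the main reason to act.

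**What to change.** 1. State in SAP section 8 which isotopologues the LC/MS assay detects. This comes first, because dividing by the unlabelled fraction when the assay already reads everything would inflate Oral F by 1.43 to 2.51 times (1/0.699 to 1/0.399).
2. In Period 1, derive the inhaled concentration per sample as LC/MS minus u × [14C]-GSK2269557 by LC+AMS, with the latter expressed as total IV parent mass and u the detected share of IV parent. Then compute Inhaled F. Before setting u, reconcile the IV activity in Protocol section 7.1 with the Synopsis and sections 5.1.2 and 5.5.2.
3. For Oral F, ML(po), Fg and the oral parent/total ratios, use the LC+AMS parent already scheduled in Period 2. Alternatively, and only if the assay reads unlabelled mass alone, divide LC/MS values by the measured unlabelled fraction of the oral batch.

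The cost is SAP wording and arithmetic on data already planned, plus the measured specific activity of each batch. Running AMS on the Period 2 parent samples costs more than the arithmetic option.
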